### 5.5.1. Screening Disposition

In the summaries below, percentages will be calculated using the number of screened patients as the denominator. Summaries will present the overall frequencies (and percentages as applicable) for the following:

- Screened patients.
- Patients randomized.
- Patients that did not meet the inclusion/exclusion criterion but were randomized (if applicable).
- Patients treated but not randomized (if applicable).
- Screen Fail patients: broken out by reason for screen failure.

### **5.5.2. Year 1 Treatment and Study Disposition**

In the summaries below, percentages will be calculated using the number of patients in the mFAS as the denominator. Summaries will present the frequencies (and percentages as applicable) by treatment group for the following:

- Patients randomized. This row will reflect the grouping based on randomization assignment.
- Patients randomized and treated.
- Patients randomized but not treated. This row will reflect grouping based on randomization assignment.
- Patients who completed the Year 1 Treatment Period.
- Patients who completed study treatment during the Year 1 Treatment Period.
- Patients who discontinued treatment during the Year 1 Treatment Period separated out by reasons for treatment discontinuation.
- Patients who enrolled in Year 2 (defined as having passed all the Inclusion/Exclusion criterion for Year 2 and signed the ICF form for Year 2).
- Patients who entered the Year 1 Follow-up Period.
- Patients who completed the Year 1 Follow-up Period.
- Patients who withdrew from the study during the Year 1 Treatment Period separated out by reasons for study withdrawal.

The same summary described above will also be provided based on the FAS.

### **5.5.3. Year 2 Disposition**

In the summaries below, percentages will be calculated using the number of patients in the SAF – Year 2 as the denominator. Summaries will present the frequencies (and percentages as applicable) by treatment group for the following:

- Patients enrolled and treated in Year 2. The treatment groups reflected in this row are based on the treatment received in Year 2 (see Section 3.4).
- Patients who completed the Year 2 Treatment Period.
- Patients who completed study treatment during the Year 2 Treatment Period.
- Patients who discontinued treatment during the Year 2 Treatment Period separated out by reason for treatment discontinuation.
- Patients who entered the Year 2 Follow-up Period.
- Patients who completed the Year 2 Follow-up Period.
- Patients who withdrew from the study during the Year 2 Treatment Period separated out by reason for study withdrawal.

## 5.6. Extent of Study Treatment Exposure and Compliance

### 5.6.1. Measurement of Compliance

#### SC Study Drug Injection

Overall treatment compliance to the SC study drug injection is defined as the actual number of SC injections divided by the expected number of SC injections during the on-treatment period (see Section 5.8) up to treatment discontinuation. It is calculated according to the following formula:

$$\frac{\text{Number of actual injections of study drug received during the treatment exposure period}}{\text{Number of planned injections of study drug during the treatment exposure period on or before the time that the patient discontinued from the treatment phase of the study}} \times 100$$

The treatment compliance to the SC study drug injection will be summarized by treatment groups with descriptive statistics for the Year 1 and Year 2 Treatment Periods separately based on the SAF – Year 1 and SAF – Year 2 respectively.

The total number of SC injections will be summarized by treatment groups with descriptive statistics for the Year 1 and Year 2 Treatment Periods based on the SAF – Year 1 and SAF – Year 2 respectively. A summary of the number (and percentage) of patients categorized by the number of SC injections received will also be included.

#### Oral Study Drug

Overall treatment compliance to oral study drug is defined as the total oral dose actually taken divided by the expected total oral dose of treatment during the treatment exposure period for Year 1 up to treatment discontinuation of the Year 1 Treatment Period. It is calculated according to the following formula based on the Naproxen/Placebo Dispensing/Accountability eCRF:

$$\frac{\sum_{\text{all treatment visits}} (\text{Number of pills dispensed} - \text{Number of pills returned})}{(\text{date of last dose of oral study drug} - \text{date of first dose of oral study drug} + 1) * 2} \times 100$$

Overall treatment compliance to oral study drug during the Year 1 Treatment Period will be summarized descriptively by treatment group based on the SAF – Year 1.

Since the oral study drug for Year 2 is naproxen prn, treatment compliance for oral study drug during the Year 2 Treatment Period is not applicable and will not be summarized.

### 5.6.3. Length of Study Observation

The length of study observation is calculated as:

*= (Date of the last study visit [up to the end of the follow-up clinic visit, including post-op joint replacement follow-up visit 2] – date of the first study drug administration in Year 1) + 1*

The total length of study participation is calculated as:

*= (Date of the last scheduled study contact [up to the end of study phone call] – date of the first study drug administration in Year 1) + 1*

The lengths of study observation and participation will be summarized by treatment group using descriptive statistics based on the SAF – Year 1 and SAF – Year 2 separately.

The number and percentage of patients with length of study observation/participation within specific time intervals will be presented by treatment group based on the SAF – Year 1 and SAF – Year 2 separately. The time intervals of interest are specified as:

- For Year 1:  $\geq 1$  day,  $\geq 29$  days,  $\geq 57$  days,  $\geq 85$  days,  $\geq 113$  days,  $\geq 141$  days,  $\geq 169$  days,  $\geq 197$  days,  $\geq 225$  days,  $\geq 253$  days,  $\geq 281$  days,  $\geq 309$  days,  $\geq 337$  days,  $\geq 365$  days,  $\geq 393$  days,  $\geq 505$  days,  $\geq 701$  days.
- For Year 2:  $\geq 365$  days,  $\geq 393$  days,  $\geq 421$  days,  $\geq 449$  days,  $\geq 477$  days,  $\geq 505$  days,  $\geq 533$  days,  $\geq 561$  days,  $\geq 589$  days,  $\geq 617$  days,  $\geq 645$  days,  $\geq 673$  days,  $\geq 701$  days,  $\geq 729$  days,  $\geq 757$  days,  $\geq 869$  days,  $\geq 1065$  days.

## 5.7. Analyses of Efficacy Variables

Unless stated otherwise, all efficacy analyses will be based on the mFAS using the Year 1 baseline value. Confidence intervals will be constructed with level of confidence equal to 95%. Models including stratifying variables will utilize the value of these variables as captured in the IWRS system.

### 5.7.1. Analysis of Primary Efficacy Variables

The co-primary efficacy variables are:

1. Change in the WOMAC pain subscale scores from baseline to week 16
2. Change in the WOMAC physical function subscale score from baseline to week 16

The following hypotheses will be tested:

- $H_{1,1}$ : There is no treatment difference between fasinumab 1 mg Q4W and placebo in WOMAC pain or physical function subscale at week 16 versus there is treatment difference in WOMAC pain and physical function subscale score at week 16
- $H_{2,1}$ : There is no treatment difference between fasinumab 1 mg Q8W and placebo in WOMAC pain or physical function subscale at week 16 versus there is treatment difference in WOMAC pain and physical function subscale score at week 16

For  $H_{1,1}$ , the estimand is the difference in means between the fasinumab 1 mg Q4W dose and placebo in the change from baseline to week 16 in the WOMAC pain and physical function scores in the mFAS, regardless of whether or not rescue medication or prohibited medication had been taken. Any data collected after discontinuing treatment in Year 1 will not be used in the primary efficacy analysis but used in a treatment policy sensitivity analysis.

The co-primary efficacy variables will be analyzed separately using a multiple imputation approach with a mixed-effect model for repeated measures (MMRM) based on the mFAS. For patients who permanently discontinued treatment due to lack of efficacy, death or AEs, their missing WOMAC subscale scores after discontinuation will be imputed with values centered at the mean baseline WOMAC subscale score of the treatment group that patient was randomized to. For patients who discontinued treatment due to other reasons (including discontinuation because of public health measures implemented in response to COVID-19), their missing WOMAC subscale scores after discontinuation will be imputed under the missing-at-random assumption using the regression method with adjustment for covariates including treatment group, randomization strata (K-L category [2 to 3, or 4], index joint [knee, hip], and geographical region [Europe, North America]) and baseline WOMAC subscale score. Intermittently missing WOMAC subscale scores prior to treatment discontinuation will be imputed using the Markov Chain Monte Carlo method.

Missing data up to week 52 will be imputed 50 times to generate 50 complete data sets by using the SAS procedure PROC MI following the 3 steps below:

- Step 1: The monotone missing pattern is induced by Markov Chain Monte Carlo (MCMC) method in MI procedure using seed number 4751611. If a randomly imputed score is imputed outside the range of the WOMAC subscale score of 0-10, then the algorithm will continue to randomly impute scores until one within the range of 0-10 is obtained.
- Step 2: The missing WOMAC subscale scores at visits subsequent to treatment discontinuation will be imputed using the regression method for the monotone pattern with seed number 4751611 and adjustment for covariates including treatment groups, randomization strata (K-L category [2 to 3, or 4], index joint [knee, hip], and geographical region [Europe, North America]), baseline WOMAC subscale score and

- all WOMAC subscale scores at preceding visits. Scores that are imputed outside the range of the WOMAC subscale will be addressed in the same manner as in step 1.
- Step 3: For patients who permanently discontinued study treatment due to lack of efficacy, death or AEs, the initially missing and now imputed WOMAC subscale scores at visits subsequent to treatment discontinuation will be adjusted to be centered at the mean baseline value for that treatment group, i.e., imputed score = initial imputed score under MAR – (mean change from baseline subscale score at the post-baseline time point for the treatment group based on patients on treatment with non-missing data at that time point).

Each imputed data set will be analyzed using a MMRM with terms for baseline WOMAC subscale score, randomization strata (K-L category [2 to 3, or 4], index joint [knee, hip], and geographical region [Europe, North America]), treatment, visit, and treatment-by-visit interaction as fixed effects. The MMRM will be fitted using the MIXED procedure in Statistical Analysis System (SAS) with an unstructured covariance matrix to model the within-patient errors. The denominator degrees of freedom will be estimated using Kenward-Roger's approximation. In the event a model cannot be fit due to the estimation algorithm failing to converge, the covariance matrix for within-patient errors will be modeled by an autoregressive 1 structure, followed by a compound symmetry structure if convergence is still not achieved for the prior.

The results from the 50 analyses will be combined using Rubin's formulae (PROC MIANALYZE). The least squares means estimates for the mean change from baseline to week 16, as well as the difference of these estimates between fasinumab and placebo will be provided along with the corresponding standard error, p-value and associated 95% confidence interval. Similar estimates at other visits will also be presented.

The hypothesis for  $H_{1,1}$  will be rejected when the p-values corresponding to the difference in change from baseline to week 16 between fasinumab 1 mg Q4W and placebo is less than the available  $\alpha_0$  (see Section 5.7.4) for both the WOMAC pain subscale score and physical function subscale score.

Since the fasinumab 1 mg Q8W treatment arm was not included in the study prior to protocol amendment 5, the estimand and analysis method for testing  $H_{2,1}$  will mimic that used for  $H_{1,1}$  with the exception that only the subset of patients in the mFAS who were randomized post amendment 5 will be utilized in the statistical analysis.

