## 10.4.3. Efficacy Analyses

## 10.4.3.1. Primary Efficacy Analysis

The primary efficacy variables will be analyzed using multiple imputation approach with a mixed-effect model for repeated measure (MMRM) based on the mFAS with adjustment for missing data due to lack of efficacy, death or AEs assuming the WOMAC scores would on average return to baseline values. A monotone missing data structure will be achieved using the MCMC option of PROC MI. Data collected after discontinuing treatment up to week 16 will not be used in the primary efficacy analysis, but used in a treatment policy sensitivity analysis. Multiple imputation for the remaining data will be based on the monotone missing data structure of the change from baseline scores using the regression imputation option in PROC MI. The missing data for patients who discontinued treatment due to other reasons will be imputed under missing-at-random assumption. The imputed data for patients discontinued from the study treatment due to lack of efficacy, death or AEs will be centered at the mean baseline value.

Missing data will be imputed 50 times to generate 50 complete data sets. Each imputed data set will be analyzed using the MMRM with terms for baseline score corresponding to the efficacy variable being analyzed, randomization strata (K-L category [2 to 3, or 4], index joint [knee, hip], and geographical region [North America, Europe]), treatment, visit, and treatment-by-visit interaction. The MMRM will be performed using the MIXED procedure in Statistical Analysis System (SAS) with an unstructured covariance matrix to model the within-patient errors. Denominator degrees of freedom will be estimated using Kenward-Roger's approximation. The results from the 50 analyses will be combined using Rubin's formulae (PROC MIANALYZE). The least-squares mean estimates for the mean change from baseline to week 16, as well as the differences of the estimates between fasinumab and placebo, and between fasinumab and naproxen, with their corresponding standard errors, p values and associated 95% confidence intervals, will be provided.

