## 2.2. Sample Size and Power Considerations

In this study, approximately 2560 patients were planned to be randomized to fasinumab 1 mg SC Q4W (840), fasinumab 1 mg SC Q8W (600), naproxen (840), or placebo (280) (see Section 5.1.3 of the protocol). This sample size was expected to provide adequate power for the comparisons between fasinumab and naproxen at week 16 for the WOMAC pain and physical function scores and the Patient Global Assessment - Osteoarthritis (PGA-OA) score and provide long term data for safety assessment.

The sample size was based on results of the WOMAC pain and physical function subscale scores and the PGA from the R475-PN-1227 study. The calculation of sample size assumed a 2-sided alpha level of 0.025 and a 15% dropout rate up to week 16 and a 30% dropout rate up to week 52. Enrollment of 840 patients in the fasinumab 1 mg Q4W group and 280 patients in the placebo group would have provided at least 99% power to detect an effect size of 0.46 in the WOMAC pain and physical function subscale scores (i.e., an absolute treatment difference of 1.1 between fasinumab and placebo and a standard deviation [SD] of 2.4 at week 16 and 52 for the full analysis set [FAS]). This sample size would have provided 99 % power to detect an effect size of 0.36 in PGA for an absolute treatment difference of 0.4 with a SD of 1.1 at week 16, and 98% power at week 52 for the FAS.

For the fasinumab 1 mg Q8W group, the 600 patients would have been compared to the approximately 200 patients in the placebo group who were enrolled after Protocol R475-OA-1611 Amendment 5 Global was implemented. For such comparisons, 2-sided alpha level of 0.025 and a 15% dropout rate up to week 16 and a 30% dropout rate up to week 52 were assumed. Additionally, the effect size for such comparisons were assumed to be 80% of the effect size for the comparison between fasinumab 1 mg Q4W group and the placebo group. Under these assumptions, enrollment of 600 patients in the fasinumab 1 mg Q8W group and 200 patients from the placebo group would have provided 97% power to detect an effect size of 0.368 ( $=0.46*80%$ ) in the WOMAC pain and physical function subscale scores at week 16 and 93% power at week 52. This sample size would have provided 84% power to detect an effect size of 0.288 ( $=0.36*80%$ ) in PGA at week 16, and 75% power at week 52 for the full analysis set (FAS).

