The sample size calculation was also based on previously reported results of the WOMAC pain subscale and physical function subscale and the PGA for naproxen (Ekman 2014) (Schnitzer 2015). Assuming a 2-sided alpha level of 0.025 and a 15% dropout rate up to week 16 and a 30% dropout rate up to week 52, an enrollment of 840 patients in the fasinumab 1 mg Q4W group and the naproxen group would have provided at least 97% power to detect an effect size of 0.22 in the WOMAC pain subscale (i.e., an absolute treatment difference of 0.51 with a SD of 2.3) at week 16, and 92% power at week 52 for FAS. This sample size would have provide 98% power to detect an effect size of 0.24 in WOMAC physical function subscale (i.e., absolute treatment difference of 0.50 with a SD of 2.1) at week 16, and 96% power at week 52 for FAS. This sample size would have provided 87% power to detect an effect size of 0.18 in PGA at week 16 between fasinumab 1 mg Q4W and naproxen for the FAS.

While the number of patients randomized was based on the sample size calculations in the protocol, the analyses of the primary and secondary efficacy endpoints will be performed at levels of significance as specified in Section 5.7.4 of this document which differs than the initial assumptions used above.

Due to regional irregularities noted in a parallel phase 3 study, the population for the primary and secondary efficacy analyses was changed in Protocol Amendment 8 Global to be performed on a modified Full Analysis Set (mFAS) that excludes patients in the randomization stratum for that region. Based on the number of patients randomized and the testing strategy specified in Section 5.7.4 it is estimated that this mFAS will provide:

- 99.9% power to detect a statistically significant difference between the 1 mg Q4W group and the placebo group in the WOMAC pain and physical function subscales at Week 16 using an alpha level of 0.05.
- 42% and 46% power to detect a statistically significant difference between the 1 mg Q8W group and the placebo group in WOMAC pain and physical function subscales, respectively, at Week 16 using an alpha level of 0.01.
- 99.9% power to detect a statistically significant difference between the 1 mg Q4W group and the naproxen group in the WOMAC pain and physical function subscales at Week 16 using an alpha level of 0.04.

As the analysis for Year 2 will be descriptive only, a targeted sample size based on power considerations was not implemented for Year 2.

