- H2,11: There is no treatment difference between fasinumab 1 mg Q8W and placebo in the WOMAC physical function subscale scores averaged across Weeks 4, 8, 12 and 16 versus there is treatment difference in the WOMAC physical function subscale scores averaged across Weeks 4, 8, 12 and 16
- H2,12: There is no treatment difference between fasinumab 1 mg Q8W and placebo in the WOMAC pain subscale scores averaged across Weeks 36, 40 and 44 versus there is treatment difference in the WOMAC pain subscale scores averaged across Weeks 36, 40 and 44
- H2,13: There is no treatment difference between fasinumab 1 mg Q8W and placebo in the WOMAC physical function subscale scores averaged across Weeks 36, 40 and 44 versus there is treatment difference in the WOMAC physical function subscale scores averaged across Weeks 36, 40 and 44

The hypotheses H1,4, H1,5, H1,6, H1,7, H1,14 and H1,15 can be tested within the same analysis method used to test H1,1 as described in Section 5.7.1. Similarly, H2,4, H2,5, H2,6 and H2,7 can be tested within the same analysis methods used to test H2,1 as described in Section 5.7.1. Additionally, the treatment policy analysis, per-protocol analysis and subgroup analyses described in Section 5.7.1 for the primary endpoint can also be utilized for the hypotheses mentioned in this paragraph.

To test H1,2, H1,8 and H1,9, a method analogous to that used to test H1,1 in Section 5.7.1 can be utilized, replacing the respective WOMAC subscale score with the PGA score. Likewise, H2,2, H2,8 and H2,9 can be tested using a method analogous to that used to test H2,1 in Section 5.7.1, replacing the respective WOMAC subscale score with the PGA score and only using the subset of patients in the mFAS randomized after protocol amendment 5 for the analyses. The multiple imputation algorithm will be modified to resample values outside the range of the PGA score (0-5) in a manner similar to the primary analysis.

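### Imputation Step 3 does not centre scores at the arm's mean baseline as SAP 5.7.1 and protocol 10.4.3.1 say it does; separately, SAP 5.7.3 resamples PGA to 0-5 on a 1-5 scale

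*SAP*

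**What the plan says.** **Stated target.** For patients who stop permanently for lack of efficacy, death or AEs, SAP 5.7.1 says "their missing WOMAC subscale scores after discontinuation will be imputed with values centered at the mean baseline WOMAC subscale score" of the randomised arm. The lead-in to Step 3 repeats that the values "will be adjusted to be centered at the mean baseline value for that treatment group". Protocol 10.4.3.1 describes the analysis as "assuming the WOMAC scores would on average return to baseline values" and says imputed data for patients who stopped "due to lack of efficacy, death or AEs will be centered at the mean baseline value". The protocol does not say which group's mean is meant; the SAP names the arm.

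**Operational rule.** Step 3 then defines the adjusted score as the missing-at-random (MAR) draw minus the "mean change from baseline subscale score at the post-baseline time point for the treatment group based on patients on treatment with non-missing data" at that visit. The draw comes from Step 2, which regresses on treatment, strata, baseline and every preceding score.

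**Reach.** Data collected after stopping treatment are left out of the primary analysis, so Step 3 sets all later values for these patients. It governs the co-primaries. Under SAP 5.7.3 the other continuous WOMAC hypotheses at weeks 16 and 44 "can be tested within the same analysis method used to test" the primary hypotheses, the PGA hypotheses use an analogous method, and the visit-averaged endpoints (H1,10 to H1,13 and H2,10 to H2,13) use the same imputation.

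**PGA.** SAP 5.7.3 resamples imputed PGA values that fall outside 0-5. Protocol 8.2.2.2 defines the scale as 1 to 5, and SAP 10.5 lists the values as 1 to 5.

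**The concern.** The words and the formula describe two different imputations. The formula removes the average improvement of patients who stayed on treatment, but the patients being adjusted may never have improved that much. A patient who stops for lack of efficacy already has a poor draw, because Step 2 conditions on poor earlier scores. Adding back the full improvement of the successful patients then overshoots baseline.

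An invented example with equal baselines shows this. Take mean baseline 6.5, mean score on treatment 3.5, and a mean draw of 5.0 among lack-of-efficacy stoppers. Step 3 gives 5.0 - (3.5 - 6.5) = 8.0, not 6.5.

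What is at stake is the meaning of the primary estimate. It would be reported as assuming a return to baseline on average, while it applies a harsher penalty that depends on outcome and whose size is not stated. If the mismatch is noticed only after unblinding, someone has to choose between two primary estimates with the results in view.

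**Working it through.** **The plan's own figure (context only).** Q4W vs placebo at week 16: 840 × 0.85 = 714 and 280 × 0.85 = 238 evaluable, difference 1.1, SD 2.4, two-sided alpha 0.025. SE = 2.4 × √(1/714 + 1/238) = 0.180; expected z = 1.1/0.180 = 6.12; power = Φ(6.12 - 2.24) = 99.99%. This agrees with the stated figure of at least 99%.

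**Algebra.** For one arm and visit, let m_D be the mean MAR draw of the lack-of-efficacy, death or AE discontinuers; y_obs and b_obs the mean visit score and mean baseline of on-treatment patients with data; and b_arm the arm's mean baseline.

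- Step 3: adjusted score = draw - (y_obs - b_obs).
- Mean adjusted score = m_D - y_obs + b_obs.
- Offset from the stated target = (m_D - y_obs) + (b_obs - b_arm).

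The sign of the shift is right: subtracting a negative change moves scores up towards baseline. The two terms could cancel, but nothing makes them do so. If stopping depends on response, the first term is positive, because m_D exceeds y_obs.

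**Illustrative size.** From the documents: difference 1.1, SD 2.4, entry pain score of at least 4, range 0-10. Assumed: baseline about 6.5 (SD 1.3); mean week-16 change -2.0 on placebo and -3.1 on fasinumab; correlation between visits 0.5 to 0.85; stops after week 8; imputation fitted within arm. Simulating Steps 2 and 3 with 15% stopping and correlation 0.7 gives:

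| Stopping | Arm | m_D | y_obs | y_obs - b_obs | Adjusted mean | b_arm | Offset |
|---|---|---|---|---|---|---|---|
| Unrelated to outcome | Placebo | 4.59 | 4.54 | -1.98 | 6.57 | 6.51 | +0.05 |
| Unrelated to outcome | Fasinumab | 3.69 | 3.51 | -3.00 | 6.69 | 6.51 | +0.17 |
| Lack of efficacy | Placebo | 6.24 | 4.21 | -2.36 | 8.59 | 6.51 | +2.08 |
| Lack of efficacy | Fasinumab | 5.31 | 3.19 | -3.37 | 8.68 | 6.51 | +2.17 |

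(Last digits differ by rounding.) Over all correlations and 5% or 15% stopping, the offset is 0.04 to 0.24 when stopping is unrelated to outcome, caused by resampling to 0-10. It is 1.4 to 3.1 when stopping is for lack of efficacy. Further runs spread the stops over weeks 4 to 12 and made the log-odds of a lack-of-efficacy stop rise by 0.4 (moderate) or 0.8 (strong) per WOMAC point. They gave 0.9 to 1.8 and 1.6 to 3.2 for lack-of-efficacy stoppers, and about 0.0 to 0.3 for AE stoppers.

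**Effect on the difference (fasinumab minus placebo, correlation 0.7).**

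- 15% lack-of-efficacy stops in both arms: -0.86 as written, -0.87 re-centred.
- 15% placebo, 5% fasinumab: as written -2.84 - (-1.65) = -1.19; re-centred -2.97 - (-1.96) = -1.01. The formula favours fasinumab by 0.18.
- Runs mixing lack-of-efficacy and AE stops: -0.02 to -0.01 at 8%/8% with the same mix; +0.04 to +0.09 in fasinumab's favour at 8% fasinumab/12% placebo.

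**Bearing on H1,1.** Removing 0.18 from the planning difference leaves z = 0.92/0.180 = 5.12 and power Φ(5.12 - 2.24) = 99.8%. These are planned full-set sizes; the SAP does not give mFAS counts by arm but states 99.9% power there at alpha 0.05.

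**PGA.** Share of accepted draws below 1 = [Φ((1-μ)/σ) - Φ(-μ/σ)] / [Φ((5-μ)/σ) - Φ(-μ/σ)]. With an assumed imputation mean of 2.0 and SD 0.7 to 1.1 this is 7.5% to 15%; with mean 3.0, 0.2% to 3%. These are draws before any Step 3 shift.

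**The case against.** The best defence is that nothing is ambiguous in execution. Step 3 gives an explicit formula, two programmers would get the same numbers, and *centred* is only a loose label. That is true, but it does not remove the contradiction: either the formula or four statements across two documents must change.

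Second, the overshoot needs outcome-related stopping. Many stops required by protocol 7.3.2.1 are triggered by safety findings rather than pain response, and for such patients the offset is near zero. This stands, and it is why the size depends on the mix of reasons.

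Third, several analyses do not rely on Step 3: the tipping-point analysis, which starts from MAR and varies the penalty for these same patients; the week-16 per-protocol analysis, which requires all doses; the subgroup models without multiple imputation; and the responder tests. The treatment-policy analysis uses it only for remaining gaps. These give context, but they do not make the description of the primary estimate correct.

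A reader might infer more than the documents support:

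- **That the formula biases the trial towards fasinumab.** The SAP assumes "a 15% dropout rate up to week 16 and a 30% dropout rate up to week 52" with no split by reason or arm, so neither the direction nor the size of a net effect is known.
- **That it materially changes the Q8W result.** The SAP states "42% and 46% power to detect a statistically significant difference between the 1 mg Q8W group and the placebo group in WOMAC pain" but not the patient numbers or effect behind it. At 42% power, standardised effects of 0.30 to 0.46 would imply anything from about 36 to 83 evaluable placebo patients, so no Q8W effect can be sized.
- **That the PGA bound shifts the PGA comparison.** No such effect has been shown.

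**Conclusion.** The mismatch between words and formula is certain, because it follows from the algebra alone. Under the formula, the mean imputed score equals the arm's mean baseline only if the two terms of the offset happen to sum to zero.

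The size is not certain. An overshoot of roughly 1 to 3 points for lack-of-efficacy stoppers, and 0 to 0.25 when stopping is unrelated to outcome, rests on assumed baselines, correlations and dropout mechanisms. The 0.18 shift in the treatment difference belongs to a deliberately lopsided case; balanced stops give about 0.01. H1,1 should survive either rule. This is worth fixing because it decides what the primary estimate means, not because it threatens the main conclusion.

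The PGA range is a plain error in the SAP. It touches H1,2, H1,8, H1,9, H2,2, H2,8 and H2,9.

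**What to change.** Before unblinding, choose one of the following.

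(a) **Make the formula match the words.** Adjusted score = MAR draw - (mean MAR draw of that arm's lack-of-efficacy, death or AE discontinuers at that visit, averaged over the 50 imputations - arm mean baseline). Averaging over imputations preserves between-imputation variation. The downside should be stated in the SAP: one pooled shift can place AE stoppers somewhat better than baseline when lack-of-efficacy stoppers pull the pooled mean up. Centring by reason group would serve as a sensitivity analysis.

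(b) **Keep the formula and correct the words.** Revise SAP 5.7.1, protocol 10.4.3.1 and the matching text in the protocol synopsis so that they no longer say the values are centred at, or return on average to, baseline. Say instead that the mean improvement of on-treatment patients in the same arm is removed from each MAR draw.

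In either case, change the PGA resampling range in SAP 5.7.3 from 0-5 to 1-5.

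Cost: a few lines of text, plus a small programming change under (a) and for the PGA bound. No new data are needed. SAP section 1 allows revision until database lock and code breaking.
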